12.2. Stopping criteria for toxicity

A patient who receives at least one dose of the study drug (PANO) per protocol is evaluable for toxicity. As shown in Table 9, the accrual will be suspended if c or more of n patients experience CTCAE (v.4) grade 3 or higher toxicity unexpected with transplant, where n is the number of evaluable patients and c is the number of patients who experience CTCAE (v.4) grade 3 unexpected toxicity or higher. Assuming true toxicity rate is 20% and the type I error rate is 5%, the stopping boundary was computed by Ivanova et al⁴⁹. If true toxicity rate is 20%, 40% and 50%, then the probability of early stopping is 4.9%, 79% and 98%, respectively.

Table 9. Boundary for early stopping rule for toxicity

n	3	4	5	6	7	8	9	10	11	12
c	3	4	4	5	5	5	6	6	6	6
n	21	22	23	24	25	26	27	28	29	30
c	9	10	10	10	11	11	11	11	12	12

Note: 1. n = # of patients who receive at least one dose of study drug

2. c = # of patients who experience CTCAE (v4) Grade 3 or higher toxicity unexpected to HCT

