12.1. Sample Size Determination

In our randomized Phase II trial of TAC and SIR vs. TAC and MTX as GVHD prophylaxis after allogeneic transplantation we observed an acute GVHD incidence of 43% (95% CI 30-63%) with TAC/SIR⁴. Simon's minimax two-stage design with 10% one-sided type I error and 10% type II error rate is used for study design as follows. We will consider 43% incidence of grade II-IV

acute GVHD (aGVHD) not warranting further study. We will use 23% incidence rate as a promising result to pursue further study. With these study parameters, 15 evaluable patients will be investigated in the first stage. If 7 or more of 15 evaluable patients experience the grade II-IV acute GVHD, the treatment will be stopped. Otherwise, once 9 or more of 15 patients completed the +90 (+/-14) days follow up without experiencing the grade II-IV acute GVHD 23 additional evaluable patients (a total of 38 evaluable patients) will be enrolled. If the number of patients experiencing the grade II-IV aGVHD is 12 or less, ($\leq 31.6\%$ incidence rate at day 100), the null hypothesis will be rejected and the regimen will be considered promising. An evaluable patient for primary endpoint is defined as patients who receive at least one dose of PANO per protocol and who neither relapse nor die of any reasons without experiencing grade II-IV aGVHD until day 100. A non-evaluable patient will be replaced and we anticipate a total of 44 patients will be accrued in order to account for 10% of competing risks (relapse or death without GVHD) at day 100.

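### The toxicity stopping probabilities in Section 12.2 fit a maximum of 38–39 patients, but about 42–44 will be dosed and counted; the printed cut-off at n=12 also does not fit the stated 4.9%

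*Combined protocol and SAP*

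**What the plan says.** Section 12.2 sets the rule: "the accrual will be suspended if c or more of n patients experience CTCAE (v.4) grade 3 or higher toxicity unexpected with transplant". Its basis is given as: "Assuming true toxicity rate is 20% and the type I error rate is 5%, the stopping boundary was computed by Ivanova et al". The resulting probabilities are: "If true toxicity rate is 20%, 40% and 50%, then the probability of early stopping is 4.9%, 79% and 98%, respectively".

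The population for this rule is broad: "A patient who receives at least one dose of the study drug (PANO) per protocol is evaluable for toxicity". The first note under Table 9 defines n in the same way. Section 12.2 states no maximum n.

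Section 12.1 plans the efficacy comparison on a smaller group: "23 additional evaluable patients (a total of 38 evaluable patients) will be enrolled". To be evaluable there, a patient must have been dosed and must be one "who neither relapse nor die of any reasons without experiencing grade II-IV aGVHD until day 100". Patients who fail this are replaced, and for that reason "we anticipate a total of 44 patients will be accrued". Section 3.3 also gives 44 for the treatment arm.

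The visible part of Table 9 covers n=3 to 12 and n=21 to 30. It shows 6 at n=12, 9 at n=21 and 11 at n=28.

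**The concern.** A patient who relapses or dies without grade II–IV acute GVHD before day 100 leaves the efficacy denominator and is replaced. That patient has still taken the study drug and stays in n for toxicity. The toxicity rule will therefore run past 38, while its stated probabilities look like those for 38.

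The error rate of a continuously monitored boundary depends on how many looks it has. If the maximum is wrong, the stated probabilities do not describe the rule as the trial will run it. Separately, one printed cut-off appears to be out of line with the rest of the table. At stake is whether those who oversee the trial have the right cut-offs, over the right range, and a correct account of how often the rule stops.

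**Working it through.** **Inputs.** Null toxicity rate 0.20, type I error 5%, stated probabilities and visible cut-offs (Section 12.2 and Table 9); 38 evaluable, 10% competing risks and 44 accrued (Section 12.1).

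**Method.** I assume a Pocock-type continuous boundary with a look after every patient. For each n, the cut-off c is the smallest count with P(X ≥ c) ≤ a, where X ~ Binomial(n, 0.20) and a is common to all n. The level a is the largest that keeps the overall crossing probability at a true rate of 0.20 at or below 0.05 over n = 1 to K. Crossing probabilities come from exact recursion: after each patient the distribution of the count is updated, and the mass at or above c is removed and added to the stopping probability.

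**Step 1: reproduce the plan's figures.**

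| Maximum K | Stop at 20% | Stop at 40% | Stop at 50% | c at n=12 | c at n=21 | c at n=28 |
|---|---|---|---|---|---|---|
| Plan | 4.9% | 79% | 98% | 6 | 9 | 11 |
| 37 | 4.97% | 77.7% | 97.2% | 7 | 9 | 11 |
| 38 | 4.93% | 79.1% | 97.7% | 7 | 9 | 11 |
| 39 | 4.93% | 79.1% | 97.7% | 7 | 9 | 11 |
| 40 | 4.97% | 79.9% | 97.9% | 7 | 9 | 11 |
| 42 | 4.97% | 82.6% | 98.6% | 7 | 10 | 12 |
| 43 | 4.97% | 82.6% | 98.6% | 7 | 10 | 12 |
| 44 | 4.94% | 83.1% | 98.7% | 7 | 10 | 12 |

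Among maxima from 25 to 49, only 38 and 39 round to all three stated figures. They agree with each other because the cut-off rises from 14 to 15 at n=39, so no new crossing is possible there. The K=38 boundary matches 19 of the 20 visible cells; the exception is n=12. The cells at n=21 and n=28 rule out a table derived for 42–44. They do not by themselves single out 38, since 37, 39 and 40 have the same values there.

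**Step 2: how many are counted.** 38 / (1 − 0.10) = 42.2, so 42–43 dosed patients at the plan's own competing-risk rate, and 44 if every anticipated accrual is dosed. The excess over 38 is about 4 to 6; 6/44 = 14% at most.

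**Step 3: the n=12 cell.** P(X ≥ 6 | n=12, 0.20) = 0.0194 and P(X ≥ 7) = 0.0039. The largest tail at any other cell of the K=38 boundary is 0.0149 (n=28), so 6 at n=12 does not meet the common level. With K=38:

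- 7 at n=12: 4.93%, 79.1%, 97.7%
- 6 at n=12: 5.23%, 79.4%, 97.7%

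The columns for n=13–20 and n=31–38 are not visible, so they were also filled in every way in which the cut-off rises by 0 or 1 per patient and stays consistent with the visible cells. None of 18,396 fills with 6 at n=12 gives 4.9%, 79% and 98%; 28 of 7,884 fills with 7 do.

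**Step 4: carry the 38-patient rule to 44 at the same level a.** The cut-offs continue as 15 at n=39–42 and 16 at n=43–44.

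- 7 at n=12: 5.19%, 83.6%, 98.7%
- 6 at n=12, as printed: 5.48%, 83.8%, 98.8%

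**Step 5: re-derive for 44.** 4.94%, 83.1%, 98.7%, with 7 at n=12, 10 at n=21, 12 at n=28 and 16 at n=44.

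**The case against.** The shifts are small and mostly towards more stopping. Going on to 44 adds about 0.3 percentage points of false stopping and raises stopping at a 40% rate from 79% to 84%. A 6 at n=12 stops slightly sooner than 7. Crossing the boundary suspends accrual; it does not automatically close the trial. All of this stands and limits the weight of the point.

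The maximum is not stated, so sizing on the efficacy-evaluable 38 is an inference, and 39 fits equally well. Likewise 44 is an anticipated accrual: Section 3.5 foresees consented patients who never start treatment, and they would not enter n. Both stand, which is why the ranges 38–39 and 42–44 are used. The two ranges do not overlap.

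The n=12 entry sits beside columns lost when the PDF was read, so it may be a reading slip. This too stands as a reason to check the source first. If the 6 is in the source, the conflict with 4.9% remains under every fill tried.

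A reader might infer that the last patients dosed go unmonitored, or that Table 9 lacks rows it should have. The documents do not support either. Where the printed table ends cannot be seen, and the missing columns are not an error in the plan. Section 11.1 has adverse events reviewed at least monthly, and Section 11.3 has the PRMC monitor safety in addition to the stopping rules.

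**Conclusion.** The point holds in a limited form. The stated 4.9%, 79% and 98%, and 19 of the 20 visible cut-offs, belong to a maximum of 38–39 patients, while the plan's own definitions put about 42–44 in the toxicity denominator. As printed and carried to 44, the rule has a type I error of about 5.5% (5.2% with 7 at n=12), above both the stated 4.9% and the 5% design limit. The printed 6 at n=12 is inconsistent with 4.9% even at a maximum of 38.

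It would be going too far to say that patients are less protected: if the rule is carried on, stopping at 40% and 50% toxicity is more likely than stated. What is wrong is a stated operating characteristic of a safety rule, by about half a percentage point at most on the error rate and about 5 points at a 40% rate.

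This rests on the assumed Pocock-type construction, which reproduces the plan's figures, on a look after each patient, and on the n=12 entry being confirmed in the source table.

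**What to change.** In Section 12.2:

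- State the maximum number of dosed patients that the rule covers; 44 agrees with Sections 3.3 and 12.1.
- Recompute Table 9 by the same method for that maximum, with cut-offs through it.
- Check the n=12 entry against the source table and correct it if it is printed as 6.
- Restate the stopping probabilities; for 44 they are about 4.9%, 83% and 99%.

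The cost is one recalculated table and one sentence. It needs no extra patients or data.

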12.3 Population for Primary and Secondary Endpoints

Patients who receive at least one dose of the study drug (PANO) per protocol will be eligible for primary and secondary endpoints.

12.4 Analysis Plan for Primary Endpoint

The cumulative incidence rate of grade II-IV acute GVHD at day 100 is the primary endpoint of the study and will be estimated along with one-sided 90%

confidence interval using the approach proposed by Gray⁵⁰. The log-log transformation will be used to compute the point-wise confidence intervals. The death and relapse will be considered as competing risks of acute GVHD.

12.5 Analysis Plan for Secondary Endpoints

The demographic and clinical characteristics of subjects will be summarized using descriptive statistics; mean, median, standard deviation and range for continuous measures and counts and frequencies for categorical measures. Adverse events will be recorded, including the details of the duration and the severity. Time-to-event data such as overall survival (OS) and relapse-free survival (RFS) is measured from the date of transplantation. OS and RFS will be analyzed using the Kaplan-Meier method⁵¹. The cumulative incidence of relapse and non-relapse mortality will be computed by Gray method. Death and relapse will be considered as the competing risks of chronic GVHD and the cumulative incidence of chronic GVHD will be measured by Gray method. The association of time-to-event data with and without competing risks will be explored by the method by Fine and Gray⁵² and the Cox proportional hazards regression model⁵³, respectively.

For correlative studies (appendix F) results will be compared to an external control patient subset that will be treated with TAC/SIR with same inclusion and exclusion criteria as this protocol except that they will not be treated with PANO. For the regulatory T-cell repopulation, the profiles of regulatory T cell counts will be analyzed using generalized linear models for repeated measures based on generalized estimating equations. The comparisons of profiles of T-cells and DC cells with external control will be made using the Satterthwaite t-test.

The analysis of the secondary endpoints is considered exploratory and no multiplicity adjustment is planned for it. A two-sided p-value of <0.05 is considered statistically significant.

If we compare a total of 30 patients (**15 in treatment group and 15 in external control**) that will achieve 83% power to detect an effect size (mean difference divided by standard deviation) of 1.1 between two groups.

If we compare a total of 40 patients (20 in PANO group and 20 in external control) will achieve 87% power to detect an effect size (mean difference divided by standard deviation) of 1 between two groups.

13 Procedures and instructions

13.1 Publication of results: Any formal presentation or publication of data from this trial may be published after review and comment by Novartis and prior to any outside submission. Novartis must receive copies of any intended

- communication in advance of publication (at least fifteen working days for presentational materials and abstracts and thirty working days for manuscripts). These requirements acknowledge Novartis' responsibility to provide peer input regarding the scientific content and conclusions of such publications or presentations. Principal Investigation/Institution shall have the final authority to determine the scope and content of its publications, provided such authority shall be exercised with reasonable regard for the interests of Novartis and, in accord with the trial contract and shall not permit disclosure of Novartis confidential or proprietary information.
- 13.2 Disclosure and confidentiality:** The investigator agrees to keep all information provided by Novartis in strict confidence and to request similar confidentiality from his/her staff and the IRB/IEC/REB. Study documents provided by Novartis (investigators' brochures and other material) will be stored appropriately to ensure their confidentiality. The information provided by Novartis to the investigator may not be disclosed to others without direct written authorization from Novartis, except to the extent necessary to obtain informed consent from patients who wish to participate in the trial.
- 13.3 Discontinuation of study:** Novartis reserves the right to discontinue any study support under the conditions specified in the clinical trial agreement.
- 13.4 Ethics and Good Clinical Practice:** This study must be carried out in compliance with the protocol and the principles of Good Clinical Practice, as described in Novartis standard operating procedures and: (1) ICH Harmonized Tripartite Guidelines for Good Clinical Practice 1996. Directive 91/507/EEC, The Rules Governing Medicinal Products in the European Community. (2) US 21 Code of Federal Regulations dealing with clinical studies (including parts 50 and 56 concerning informed consent and IRB regulations); and (3) Declaration of Helsinki and amendments, concerning medical research in humans (Recommendations Guiding Physicians in Biomedical Research Involving Human Subjects). The investigator agrees to adhere to the instructions and procedures described in it and thereby to adhere to the principles of Good Clinical Practice that it conforms to.
- 13.5 Institutional Review Board/Independent Ethics Committee.** Before implementing this study, the protocol, the proposed informed consent form and other information to subjects, must be reviewed by a properly constituted Institutional Review Board/Independent Ethics Committee/Research Ethics Board (IRB/IEC/REB). A signed and dated statement that the protocol and informed consent have been approved by the IRB/IEC/REB must be given to Novartis before study initiation. Any amendments to the protocol, other than administrative ones, must be reviewed by Novartis approved by this committee.

13.6 Informed consent. The investigator must explain to each subject (or legally authorized representative) the nature of the study, its purpose, the procedures involved, the expected duration, the potential risks and benefits involved and any discomfort it may entail. Each subject must be informed that participation in the study is voluntary and that he/she may withdraw from the study at any time and that withdrawal of consent will not affect his/her subsequent medical treatment or relationship with the treating physician.

This informed consent should be given by means of a standard written statement, written in non-technical language. The subject should read and consider the statement before signing and dating it, and should be given a copy of the signed document. If the subject cannot read or sign the documents, oral presentation may be made or signature given by the subject's legally appointed representative, if witnessed by a person not involved in the study, mentioning that the patient could not read or sign the documents. No patient can enter the study before his/her informed consent has been obtained.

The informed consent form is considered to be part of the protocol, and must be submitted by the investigator with it for IRB/IEC/REB approval.

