We will also measure serum levels of soluble IL-2 receptor α using a commercially available ELISA kit. Test will be done before PANO administration on day 30 to -5, 15(+/-3) and 28(+/-3). Data for inflammatory cytokines from the whole study population will be presented over time and compared to data from similar external control patients

treated TAC/SIR with identical inclusion and exclusion criteria except that will not be treated with PANO.

GVHD Biomarkers

ELISA-based analysis will be used to determine whether a marker panel comprised of IL-2R α , TNFR1, HGF, IL-8, Elafin, REG-3 α and ST2 levels tested prospectively at 30 to -5, and 15(+/-3) after allogeneic HCT is able to predict for the development of acute GVHD. Test will be done before PANO administration on day -30 to 5, and on days 15+/-1. Data for GVHD biomarkers from the whole study population will be presented over time and compared to data from similar external control patients treated TAC/SIR with identical inclusion and exclusion criteria except that will not be treated with PANO.

Stat-3 activation and acetylation, STAT-5 and S6 phosphorylation

To determine the functional impact of HDACi on PBMCs we will measure total STAT-3, phosphorylated STAT3 and acetylated STAT-3 by WB and flow cytometry in PBMC and gated T/DCs cells populations in patients and external controls on day 30 to -5, 15(+/-3), 28(+/-3), 90(+/-14) and 365(+/-45). T-cell STAT5 and S6 phosphorylation will also be measured among the external controls on day +30+/-3 and day +90+/-314. Data for stat-3/stat-5 and S6 phosphorylation and/or acetylation subset from the whole study population will be presented over time and compared to data from similar external control patients treated TAC/SIR with identical inclusion and exclusion criteria except that will not be treated with PANO.

Note: The data gathered on these results will be used for future analysis not considered in the context of this proposal. Thus, after identifying changes in phenotype and the expression pattern of immune-related genes upon PANO/TAC/SIR treatment, we will expand our research to investigate the role of PANO in their regulation.

List of Test to be performed in patients treated with TAC+SIR+PANO and “external control patients” treated with TAC+SIR only:

TEST	-30 to -5	15(+/-3)	28(+/-3)	90(+/-14)	365(+/-45)
ImmuneReconstitution (T, DCs and Tregs)	x	x	x	x	x
Histone Acetylation (T and DCs)	x	x	x	x	x
STAT-3 activation and acetylation	x	x	x	x	x

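### Section 12.5 plans GEE for Treg profiles with at most 20 controls and no small-sample correction; an uncorrected sandwich Wald test of group-by-visit would have about 10–13% type I error at a nominal 5%.

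*Combined protocol and SAP*

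**What the plan says.** Section 12.5 (Analysis Plan for Secondary Endpoints) opens its correlative paragraph by saying that results will be compared with an external control group given TAC/SIR without panobinostat. Treg counts then get a method of their own: the profiles of "regulatory T cell counts will be analyzed using generalized linear models for repeated measures based on generalized estimating equations". The following sentence reads "The comparisons of profiles of T-cells and DC cells with external control will be made using the Satterthwaite t-test". The threshold is "A two-sided p-value of <0.05 is considered statistically significant", and the secondary analyses are labelled exploratory with no multiplicity adjustment.

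Two power statements follow. One takes "15 in treatment group and 15 in external control" and gives "83% power to detect an effect size (mean difference divided by standard deviation) of 1.1 between two groups". The other reads "If we compare a total of 40 patients (20 in PANO group and 20 in external control) will achieve 87% power", at an effect size of 1.

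Section 3.3 plans 44 treated patients and 20 external controls. Appendix F says the whole treated population will be compared with those controls. The test list in Appendix F, in the row "ImmuneReconstitution (T, DCs and Tregs", marks five sampling times: pre-treatment, then days 15, 28, 90 and 365.

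Neither section states the GEE variance estimator, working correlation, link, contrast, Wald or score form, or reference distribution.

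**The concern.** The GEE sandwich covariance is a large-sample estimator. With few independent patients it is biased downwards, and the chi-square reference takes no account of the uncertainty in estimating it. Both effects make the test reject too often, and the excess grows with the degrees of freedom of the contrast. The number that matters is patients per group, not samples, and here one group has at most 20.

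Treg recovery is the mechanism put forward in the rationale (Section 1.4). The objectives table in Section 2.2 asks whether panobinostat raises Treg numbers, and Section 1.4 says the trial is meant to screen for biologic as well as clinical activity. A Treg p-value below 0.05 would be read as support for that mechanism, so it should mean what it says.

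**Working it through.** **Inputs from the documents.** Two-sided alpha 0.05; power scenarios of 15 v 15 and 20 v 20 (Section 12.5); 44 treated and 20 controls (Section 3.3); five visits (Appendices C and F). Group-by-visit therefore has (2−1)×(5−1) = 4 degrees of freedom.

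**Assumptions not in the documents.** Normal data, equal variances, complete visits, identity link, separate means for each group and visit. Simulations use a within-patient correlation of 0.5. The exact results below do not depend on the correlation, and simulations with AR(1) correlation 0.7 were similar.

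**Step 1: the plan's own power figures.** Two-sample t-test, noncentrality d×√(n/2):
- n=15, d=1.1: 1.1×√7.5 = 3.012; critical t on 28 df = 2.048; power 82.8% (plan: 83%).
- n=20, d=1.0: √10 = 3.162; critical t on 38 df = 2.024; power 86.9% (plan: 87%).

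Both reproduce, as t-test figures. They are not GEE power figures.

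**Step 2: size of the uncorrected sandwich Wald test.** With equal groups and complete data, the sandwich covariance of the group difference is (n−1)/n times the unbiased one. The Wald statistic is therefore n/(n−1) times Hotelling's T² on ν = 2n−2 df. For a p-df contrast,

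size = P( F(p, ν−p+1) > χ²(0.95, p) × (n−1)/n × (ν−p+1)/(νp) ).

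- p=4, n=15: 9.488 × 14/15 × 25/112 = 1.977; P(F(4,25) > 1.977) = 12.9%.
- p=4, n=20: 9.488 × 19/20 × 35/152 = 2.076; P(F(4,35) > 2.076) = 10.5%.
- p=1, n=15: 3.841 × 14/15 = 3.585; P(F(1,28) > 3.585) = 6.9%.
- p=1, n=20: 3.841 × 19/20 = 3.649; P(F(1,38) > 3.649) = 6.4%.

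A joint 5-df test of any group difference gives 15.7% and 12.3%. Fitting GEE with exchangeable working correlation to simulated data (1,500 runs per setting) gave 12.6% and 10.5% for the 4-df test, and 7.5% and 7.8% for a 1-df test (Monte Carlo standard error about 0.7 points).

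**Step 3: other settings, by simulation.** With 44 v 20 and normal data the 4-df test has about 10% error. With lognormal data it has 10.9% (15 v 15), 8.6% (20 v 20) and 7.8% (44 v 20). A second set of lognormal runs (log-scale standard deviation 1) gave 10.2%, 8.2% and 7.4%. A robust score test, instead of a Wald test, gave about 4%.

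**Step 4: what corrects it.** In the balanced case the Kauermann–Carroll covariance equals the unbiased one, and the Mancl–DeRouen covariance is n/(n−1) times that. The scaled F reference is νp/(ν−p+1) × F(p, ν−p+1), with ν = n₁+n₂−2.

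| 4-df group-by-visit test | 15 v 15 | 20 v 20 |
|---|---|---|
| Uncorrected, chi-square | 12.9% | 10.5% |
| Kauermann–Carroll, chi-square | 10.9% | 9.1% |
| Mancl–DeRouen, chi-square | 9.0% | 7.8% |
| Kauermann–Carroll, scaled F | 5.0% | 5.0% |
| Mancl–DeRouen, scaled F | 4.0% | 4.2% |

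For a 1-df contrast with a t reference, Kauermann–Carroll gives 5.0% at both sizes and Mancl–DeRouen 4.3% and 4.5%. At 44 v 20 (simulated), the 4-df test with scaled F gives 6.3% with Kauermann–Carroll and 5.5% with Mancl–DeRouen. Correcting the covariance while keeping the chi-square reference is not enough for the 4-df test.

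**The case against.** The strongest reply is that the plan never says it will use uncorrected errors. It is silent on the variance estimator and the contrast, and silence is not a choice of the worst option. That stands, and it is why the conclusion is conditional. But an uncorrected sandwich Wald test is the usual way of running GEE, and nothing in Section 12.5 rules it out.

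Second, GEE may not be the between-group test at all. Tregs are T cells, the next sentence gives T-cell comparisons with external controls to the Satterthwaite t-test, which is a small-sample method, and the power figures match a t-test. This reading is tenable. The other is equally so: Tregs have their own sentence and method inside a paragraph about the external controls. The plan should say which applies.

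Third, 15 v 15 and 20 v 20 are conditional power scenarios, while Appendix F uses all treated patients. That is right, but a larger treated group does not help much with 20 controls: 44 v 20 still gives about 10%.

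Fourth, the analysis is exploratory, unadjusted for multiplicity and non-randomised, so its p-values are already weak evidence. That stands and limits the weight of the point.

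A reader might also infer bias from late samples lost to death or relapse. The documents do not say that sampling stops at relapse, Section 8.7 continues correlative studies after panobinostat is stopped for GVHD, and no such bias has been quantified here. Nor is a switch to a mixed model required: it would not resolve truncation by death, and corrected GEE is adequate.

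**Conclusion.** The concern holds conditionally. If Treg profiles are compared by GEE with the usual uncorrected sandwich Wald test, type I error at a nominal 5% is about 10–13% for the 4-df group-by-visit test (about 9–11% with lognormal data at 15–20 per group) and about 6–7% for a 1-df contrast. This rests on complete visits, an identity link and, for the main figures, normal data with equal variances.

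A reader might infer that every 5% test in this analysis at least doubles its error rate. That is not supported. One-df contrasts are only mildly inflated, a score test is not inflated, and the lognormal results at 20 v 20 and 44 v 20 fall below 10%. An interval for a single contrast would cover about 93–94%, since 100 − 6.9 = 93.1 and 100 − 6.4 = 93.6.

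The rule in Section 12.1 (12 or fewer events in 38 patients) does not use any Treg result, so the primary conclusion is untouched.

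**What to change.** In Section 12.5, keep GEE and add three specifications:

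1. A bias-corrected covariance (Mancl–DeRouen or Kauermann–Carroll) with a t reference for 1-df contrasts and a scaled F reference for multi-df tests. Mancl–DeRouen stays closer to 5% when the groups are as unequal as 44 v 20.
2. The contrast to be tested, for example group-by-visit over the five sampling times, together with the link and working correlation.
3. Whether GEE or the Satterthwaite t-test is the Treg comparison with external controls, and which of these the quoted power refers to.

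No change is needed to include all treated patients; Appendix F already does so.

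The cost is a few lines of wording and somewhat wider intervals. For a 1-df contrast, Mancl–DeRouen with t widens the interval by a factor of n/(n−1) × t/1.960. That is 15/14 × 2.048/1.960 = 1.12 at 15 per group and 20/19 × 2.024/1.960 = 1.09 at 20. Kauermann–Carroll uses √(n/(n−1)) in place of n/(n−1), giving 1.08 and 1.06.

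### The T-cell and DC comparison with non-randomized external controls rests on a t-test that cannot adjust for donor type or conditioning, and the tested value and time point are not named

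*Combined protocol and SAP*

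**What the plan says.** Section 12.5 gives two methods for the cell data. For regulatory T cells, "profiles of regulatory T cell counts will be analyzed using generalized linear models for repeated measures based on generalized estimating equations". For the comparison with controls, "The comparisons of profiles of T-cells and DC cells with external control will be made using the Satterthwaite t-test". No covariate, change score, summary measure or time point is attached to the t-test. The section calls the secondary analyses exploratory and plans no multiplicity adjustment, but adds that "A two-sided p-value of <0.05 is considered statistically significant".

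The power statement has two scenarios. With "15 in treatment group and 15 in external control", the comparison "will achieve 83% power to detect an effect size (mean difference divided by standard deviation) of 1.1 between two groups". The second reads "20 in PANO group and 20 in external control) will achieve 87% power to detect an effect size" of 1.

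Section 3.1 describes a single-arm, non-randomized study in which only the correlative results are compared with external controls. The controls receive TAC/SIR under the same eligibility criteria. Section 3.3 plans 20 controls, accrued alongside the treated patients at 0.5 per month. Section 4.1.10 admits related and unrelated 8/8 matched donors. Section 5.2 leaves the choice between myeloablative and reduced-intensity conditioning to the physician.

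In the Appendix F test list, which applies to both groups, the row beginning "ImmuneReconstitution (T, DCs and Tregs" is marked at day -30 to -5 and at days 15, 28, 90 and 365. Histone acetylation and STAT-3 follow the same five-point schedule.

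**The concern.** The correlative comparison is the only between-group comparison in the trial. It is meant to show whether panobinostat changed immune reconstitution. Shared eligibility criteria do not make the groups alike, because each criterion admits a mix: two donor types and two conditioning intensities. Either could plausibly influence cell recovery. If the mix differs between groups, an unadjusted difference in means combines the drug effect with the case-mix effect, and a p-value below 0.05 would be called significant either way.

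The same section already plans a repeated-measures model for one subset, regulatory T cells, and gives no reason for treating the other T-cell subsets and DCs differently. It also does not say which value enters the t-test or at which visit. The main comparison for those measures is therefore not fixed in advance.

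**Working it through.** **Inputs from the documents.** Two-sided alpha 0.05; 15 vs 15 at effect size 1.1 and 20 vs 20 at effect size 1.0, with stated power 83% and 87% (12.5). Planned sizes are 38 evaluable patients (12.1), 44 treated and 20 controls (3.3). At 0.5 controls per month over the stated 24 months, 0.5 × 24 = 12 controls, so 12 to 20 is the realistic range.

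**Assumptions, not in the documents.** The case-mix split, the size of its effect, and the correlation r between the pre-treatment and later values.

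**1. The plan's own power.** Two-sample t-test, df = n1 + n2 − 2, noncentrality = d / √(1/n1 + 1/n2).
- 15 vs 15: 1.1 / 0.3651 = 3.01, df 28, power 82.8% (stated 83%).
- 20 vs 20: 1.0 / 0.3162 = 3.16, df 38, power 86.9% (stated 87%).

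Both figures reproduce with one unadjusted value per patient, so the power statement allows for no covariates and no repeated samples.

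**2. Case mix read as a drug effect.** Assume 70% vs 40% have a conditioning type that shifts the measure by 0.7 SD, with no drug effect. The expected difference is (0.70 − 0.40) × 0.7 = 0.21 SD. Noncentrality = 0.21 / √(1/n1 + 1/n2). The last two columns are simulations (8,000 runs each, residual SD 1, case mix drawn at random). The adjusted linear model contains group, conditioning, donor type and a baseline value.

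| Treated vs control | Noncentrality | Rejection, formula | Satterthwaite t-test, simulated | Adjusted model, simulated |
|---|---|---|---|---|
| 15 vs 15 | 0.575 | 8.6% | 8.4% | 5.1% |
| 20 vs 20 | 0.664 | 9.9% | 9.6% | 4.8% |
| 38 vs 12 | 0.634 | 9.5% | 9.8% | 5.0% |
| 38 vs 20 | 0.760 | 11.6% | 11.2% | 5.4% |
| 44 vs 20 | 0.779 | 12.0% | 11.3% | 5.1% |

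**3. What the pre-treatment value adds.** Adjustment at one visit multiplies the variance by 1 − r² and costs one degree of freedom.

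| Assumed r | 1 − r² | Power, 15 vs 15 | Power, 20 vs 20 |
|---|---|---|---|
| 0 | 1.00 | 82.7% | 86.8% |
| 0.2 | 0.96 | 84.2% | 88.2% |
| 0.3 | 0.91 | 86.1% | 89.8% |
| 0.5 | 0.75 | 91.8% | 94.5% |

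At r of 0.2 to 0.3 the gain is about 1 to 3 points. The bias that a baseline imbalance leaves in the unadjusted difference is r × imbalance. An imbalance of 0.5 SD with r = 0.3 leaves 0.15 SD, and a rejection rate of 6.8% (15 vs 15) or 7.5% (20 vs 20). At r near zero there is neither gain nor bias from this source.

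**4. Does the obvious replacement hold its level?** A GEE with the terms proposed below, independence working correlation and the standard sandwich variance was simulated with no group effect (3,000 runs per setting; between-visit correlation 0.3 to 0.7, baseline correlation 0.2; sizes 15 vs 15, 20 vs 20, 38 vs 12 and 44 vs 20). The joint test of group differences over the four visits rejected in about 10 to 16% of runs, and the average group effect in about 6 to 10%. An uncorrected GEE is therefore not adequate at these sizes.

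**The case against.** The analysis is declared exploratory, cannot change the primary endpoint or the two-stage decision, and already gives regulatory T cells, the subset closest to the hypothesis, a repeated-measures model. Identical eligibility and concurrent accrual limit the differences between groups. The Satterthwaite test is a sound choice for unequal variances and group sizes. All of this stands and keeps the priority low. None of it adjusts for donor type or conditioning, however, and exploratory status does not remove confounding.

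Two stronger readings are tempting and should not be made.

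- **That the plan discards the pre-treatment and repeated samples.** It does not say so. A t-test on change from baseline, or on a per-patient summary over visits, is compatible with the wording. The defensible statement is that the tested quantity is unspecified. The value of the baseline may also be slight, since the first sample is the recipient's own blood and later cells are mostly donor-derived, so r may be near zero.
- **That four t-tests per subset give an 18.5% false-positive risk.** The number of tests is not stated, and the section openly declines multiplicity adjustment. The figure 1 − 0.95⁴ = 18.5% also assumes independent tests, so it is an upper bound. With between-visit correlations of 0.3 to 0.7, simulation gives about 12 to 18%.

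**Conclusion.** The point holds for non-Treg T-cell subsets and DCs. The only named between-group method cannot adjust for donor type or conditioning intensity in a non-randomized comparison, and neither the use of the pre-treatment value nor the time point is specified. The harm is confounding: about 8 to 12% rejection at a nominal 5% under the assumed 70% vs 40% split and 0.7 SD shift, against about 5% after adjustment. Those two inputs are illustrative. A smaller imbalance or shift brings the rate towards 5%, and a larger one raises it. The power gained from the baseline value is a secondary benefit, about 1 to 3 points at an assumed correlation of 0.2 to 0.3. A reader might infer that the trial's main conclusion is at risk, but it is not: the primary endpoint does not use the external controls.

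**What to change.** In section 12.5, make a longitudinal model the main comparison for each non-Treg T-cell and DC measure, and for the acetylation and STAT-3 measures on the same schedule. Use either a linear mixed model with Kenward-Roger degrees of freedom or a GEE with a small-sample variance correction. Include group, time, group-by-time, the day -30 to -5 value, donor type (related or unrelated) and conditioning intensity (myeloablative or reduced). Name one contrast as the main one: either the group difference at one stated visit or the average post-transplant group difference. Keep the Satterthwaite t-test as descriptive and state which value it uses.

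The cost is SAP wording, somewhat more analysis, and a few degrees of freedom with 12 to 20 controls, so the covariate list should stay this short. No new samples or visits are needed, but donor type and conditioning must be recorded for the controls as well as the treated patients.
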